## 4.4 General Guidelines

Following registration, patients should begin protocol treatment within 7 days. Issues that would cause treatment delays should be discussed with the Principal Investigator. If a patient does not receive protocol therapy following registration, the patient's registration on the study may be canceled. The Study Coordinator should be notified of cancellations as soon as possible.

## 5. TREATMENT PLAN

# 5.1 Agent Administration

Treatment will be administered on an outpatient basis. Reported adverse events and potential risks are described in Section 7. Appropriate dose modifications are described in Section 6. No investigational or commercial agents or therapies other than those described below may be administered with the intent to treat the patient's malignancy.

Regimen Description					
Agent	Premedications; Precautions	Dose	Route	Schedule	Cycle Length
Nivolumab	None	in 100 ml NS	IV over 60 minutes (+/- 10 minutes)	Every 2 weeks	14 days
**Doses as appr	opriate for assigned do	se level.	· · · · ·		

A flat dose of 240 mg will be administered. There will be no dose modifications allowed.

Nivolumab is to be administered as a 60-minute (+/- 10 minutes) IV infusion, using a volumetric pump with a 0.2/1.2 micron in-line filter at the protocol-specified dose. The drug can be diluted with 0.9% normal saline for delivery but the total drug concentration of the solution cannot be

below 1.0 mg/mL. It is not to be administered as an IV push or bolus injection. At the end of the infusion, flush the line with a sufficient quantity of normal saline.

# 5.2 General Concomitant Medication and Supportive Care Guidelines

## 5.2.1 Supportive Care

All supportive measures consistent with optimal patient care will be given throughout the study.

See Section 5.1 for supportive care considerations for nivolumab administration.

Patients requiring chemotherapy or radiation therapy during the study will be taken off study treatment. Any exceptions must be discussed with the Principal Investigator.

## 5.2.2 Other Medications

Recommended prophylaxis for opportunistic infections includes Bactrim DS every other day. Subjects must be instructed to inform the investigators of the current or planned use or all other medications during the study (including prescription medications, over-the-counter medications, vitamins and herbal and nutritional supplements). It is the responsibility of the investigator to ensure that details regarding all medications are documented. Bisphosphonates started prior to screening activities or initiated during the course of the study to control bone pain may be used with caution.

Prophylactic growth factor (G-CSF) administration is not recommended. Based on observed toxicities, protocol-specified dose modification guidelines should be followed for subsequent therapy cycles. Management of anemia will be at the discretion of the treating physician, No concurrent investigational agents are permitted.

# **5.2.3 Prohibited Therapies**

Patients in this study may not use vaccines for the treatment of cancer for up to one month pre and post dosing with nivolumab. Concomitant systemic or local anti-cancer medications including biologics, or radiation therapy treatments are prohibited in this study while receiving nivolumab.

Patients may not use any of the following therapies during the study:

- Any non-study anti-cancer agent (investigational or non-investigational)
- Any other investigational agents
- CTLA4 antagonists, CD137 agonists, PD-1 inhibitors
- Immunosuppressive agents, unless indicated to manage study therapy induced immunerelated adverse events (irAEs)
- Chronic systemic corticosteroids, unless indicated to manage study therapy induced irAEs or chronic graft-versus-host disease (GVHD) at a stable dose prior to study entry

• Any non-oncology vaccine therapies used for the prevention of infectious diseases (for up to 30 days prior to or after any dose of study drug, however it is suggested that routine vaccinations, including seasonal influenza, be given at least 2 weeks prior to study treatment).

## 5.3 **Duration of Therapy**

In the absence of treatment delays due to adverse event(s), treatment may continue for the 4 starting doses plus 42 cycles (approximately 23 months) or until one of the following criteria applies:

- Disease progression,
- Intercurrent illness that prevents further administration of treatment,
- Patient decides to withdraw from the study,
- General or specific changes in the patient's condition render the patient unacceptable for further treatment in the judgment of the investigator, or
- Unacceptable adverse event(s) which include the following (see also Section 6 for dosing delays/dose modifications and Appendix E for specific algorithms):
  - Any toxicity requiring high dose corticosteroids except patients with grade 2 or 3 skin lesions, pruritis, thyroiditis, or n. VII palsy can be restarted after a tapered dose of corticosteroids.
  - Any dosing interruption lasting more than 6 weeks, with the following exceptions:
    - Patients being tapered after high dose corticosteroids over one month followed by a two-week observation period will be allowed an additional two weeks to restart treatment (a maximum eight week interruption).
    - Dosing interruptions more than 6 weeks that occur for non-drug-related reasons may be allowed if approved by the Principal Investigator. Prior to re-initiating treatment in a subject with a dosing interruption lasting more than 6 weeks, the Principal Investigator must be consulted.
  - Any adverse event, laboratory abnormality, or intercurrent illness which, in the judgment of the investigator, presents a substantial clinical risk to the subject with continued study drug dosing
  - Requiring additional immune suppressive treatment beyond steroids

Tumor assessments should continue as per protocol even if dosing is interrupted.

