## 5.6 Criteria to Resume Treatment

Some patients may continue to benefit from treatment, maintaining or improving responses after progression including those treated with steroids.

Restarting applies only to Grade 2 events and some Grade 3 events (skin rash and thyroiditis).

For non-autoimmune or non-inflammatory events, patients may resume treatment with study drug when the drug-related AE(s) resolve to Grade  $\leq 1$  or baseline value, with the following exceptions:

- Patients may resume treatment in the presence of Grade 2 fatigue.
- Evaluation to exclude any additional immune mediated events endocrine, GI, and liver / pancreas function as clinically indicated must be made prior to restarting.
- Non-drug-related toxicity including hepatic, pulmonary toxicity, diarrhea, or colitis, must have resolved to baseline before treatment is resumed.

If the criteria to resume treatment are met, the patient should restart treatment no sooner than the next scheduled time point per protocol. However, if the treatment is delayed past the next scheduled time point per protocol the treatment should resume at the earliest convenient point that is within the 6 week delay period.

If treatment is delayed for > 6 weeks, (> 8 weeks for patients on a steroid taper), the patient must be permanently discontinued from study therapy, except as specified in Section 5.3.

For patients treated with corticosteroids:

- Grade 2 events must resolve to  $\leq$  Grade 1 before considering retreatment.
- Grade ≥ 2 events should have nivolumab held until resolution to ≤ Grade 1 for at least 2 weeks following complete removal from steroid treatment except for maintenance replacement doses for adrenal insufficiency (preferably no greater than 10mg prednisone equivalent daily).
- Grade  $\geq$  3 events should have nivolumab discontinued. Patients with Grade 3 thyroiditis and skin rash may continue therapy as for Grade 2 events with resolution and stable

replacement treatment.

Patients with hepatitis, pancreatitis, pneumonitis, and colitis are at risk for exacerbation with retreatment if there is residual inflammation and should resolve to Grade 0 or baseline before retreatment. Baseline can mean the initial grade *i.e.* Grade <1 where permitted on study.

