#### 6. DOSING DELAYS/DOSE MODIFICATIONS

There will be no dose adjustments allowed. Subjects with infusion delays > 49 days (i.e., 2 missed doses + 7 days) should discontinue the study drugs.

Please refer to Appendix E to the protocol for toxicity management algorithms which include specific treatment guidelines. These algorithms should be followed unless there are specific clinical circumstances which the treating physician indicates variations or alternative treatment is needed.

Generally, we strongly encourage early evaluation, withholding drug, and appropriate treatment as indicated in the management tables and following event specific guidelines.

ALL OTHER	ALL OTHER Management/Next Dose for Nivolumab	
EVENTS*	*Not agent related, or agent related non-immunologically mediated	
$\leq$ Grade 1	No change in dose.	
Grade 2	Hold until $\leq$ Grade 1 OR baseline. Resume at same dose level.	
Grade 3	Hold until $\leq$ Grade 1 continue at investigator discretion.	
Grade 4	Off protocol therapy.	
Recommended management: As clinically indicated.		

ALL OTHER	Management/Next Dose for Nivolumab	
EVENTS**	**Immunologically mediated	
$\leq$ Grade 1	No change in dose.	
Grade 2	Hold until $\leq$ Grade 1 OR baseline. When resolved, resume at same dose level.	
Grade 3	Off protocol therapy (exceptions noted in Section 5.3 )	
Grade 4	Off protocol therapy	
Recommended management: As clinically indicated.		

Skin Rash and Oral Lesions	Management/Next Dose for Nivolumab
$\leq$ Grade 1	No change in dose.*
Grade 2	No change in dose.* May continue on treatment at investigator discretion.
Grade 3	Hold* until $\leq$ Grade 1. Resume at same level at investigator discretion.
Grade 4	Off protocol therapy.

\*Patients with purpuric or bullous lesions must be evaluated for vasculitis, Steven-Johnson syndrome, TEN, and autoimmune bullous disease including oral lesions of bullous pemphigus/pemphagoid. Pruritus may occur with or without skin rash and should be treated symptomatically if there is no associated liver or GI toxicity. Note skin rash typically occurs early and may be followed by additional events particularly during steroids tapering.

Recommended management: See Appendix E for Skin AE management algorithm.

Liver Function AST, ALT, Bilirubin	Management/Next Dose for Nivolumab
$\leq$ Grade 1	No change in dose. May continue on treatment at investigator discretion.

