Grade 2	Hold until UNL or baseline. Resume at same dose level. Consider steroid treatment > 7 days.
Grade 3	Off protocol therapy.
Grade 4	Off protocol therapy.
Continued treatment	nt of active immune mediated hepatitis may exacerbate ongoing inflammation. Holding

drug to evaluate LFT changes and early treatment are recommended.

LFT changes may occur during steroid tapers from other events and may occur together with other GI events including cholecystitis/pancreatitis.

For individuals who are hepatitis B or C positive, viral DNA or RNA load, respectively, should be measured to determine if worsening LFTs are due to immune-mediated hepatitis or infectious hepatitis. Recommended management: See Appendix E for Hepatic AE management algorithm.

Diarrhea/ Colitis	Management/Next Dose for Nivolumab
$\leq$ Grade 1	Hold until Grade 0 or baseline. When resolved, resume at same dose level.
Grade 2	Hold until Grade 0 or baseline. Consider steroid treatment > 7 days.
Grade 3	Off protocol therapy.
Grade 4	Off protocol therapy.
Patients with Grade 2 symptoms but normal colonoscopy and biopsies may be retreated after resolution.	
Patients who require steroids should be taken off study treatment.	
Please evaluate pituitary function prior to starting steroids if possible without compromising acute care.	
Evaluation for all patients for additional causes includes C. diff, acute and self-limited infectious and food	
borne illness, ischemic bowel, diverticulitis, and IBD.	

Recommended management: See Appendix E for GI AE management algorithm for management of symptomatic colitis.

Pancreatitis Amylase/Lipase	Management/Next Dose for Nivolumab
$\leq$ Grade 1	If asymptomatic without evidence of pancreatitis, liver or gallbladder disease, or new onset diabetes, may continue on treatment at investigator discretion.
Grade 2	If asymptomatic without evidence of pancreatitis, liver or gallbladder disease, or new

Pancreatitis Amylase/Lipase	Management/Next Dose for Nivolumab
	onset diabetes, may continue on treatment at investigator discretion.
Grade 3	If symptomatic, hold until Grade 0. If asymptomatic, without clinical, radiographic, or ultrasound evidence of pancreatitis, and no evidence of associated liver or gall bladder disease or new onset diabetes, may continue on treatment at investigator's discretion. Patients who develop symptomatic pancreatitis or DM should be taken off protocol therapy.

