Patients with Grad	e 2 or 3 N-V should be evaluated for upper GI inflammation and other immune related

Other GI N-V	Management/Next Dose for Nivolumab
events.	

Fatigue	Management/Next Dose for Nivolumab
$\leq$ Grade 1	No change in dose.
Grade 2	No change in dose.
Grade 3	Hold until $\leq$ Grade 2. Resume at same dose level.
Grade 4	Off protocol therapy
	common adverse event associated with immune checkpoint therapy. Grade 2 or greater
fatigue should be	evaluated for associated or underlying organ involvement including pituitary, thyroid,
and hepatic, or muscle (CPK) inflammation.	

Neurologic Events	Management/Next Dose for Nivolumab
$\leq$ Grade 1	Hold dose pending evaluation and observation. When resolved, resume with no change in dose. *
Grade 2	Hold dose pending evaluation and observation. Hold until $\leq$ Grade 1.*Off protocol therapy if treatment with steroids is required. When resolved, resume at same dose level for peripheral isolated n. VII (Bell's palsy)
Grade 3	Off protocol therapy.
Grade 4	Off protocol therapy.
*Patients with any CNS events including aseptic meningitis, encephalitis, symptomatic hypophysitis, or myopathy, peripheral demyelinating neuropathy, cranial neuropathy (other than peripheral n. VII), GB syndrome, myasthenia gravis should be off study.	
Recommended man	agement: See Appendix E for Neurologic AE management algorithm.

Endocrine Hypophysitis Adrenal Insufficiency	Management/Next Dose for Nivolumab
< Grade 1	With asymptomatic TSH elevation may continue on study with appropriate
	evaluation, and endocrine consultation suggested.*
	Hold until patients are on a stable replacement hormone regimen. If treated with
Grade 2	steroids patients must be stable off steroids for two weeks. Resume at same dose
	level.
Grade 3	Off protocol therapy.
Grade 4	Off protocol therapy.

Note all patients with symptomatic pituitary enlargement, exclusive of hormone deficiency, but including severe headache or enlarged pituitary on MRI should be considered Grade 3 events. Isolated thyroid or testosterone deficiency may be treated as Grade 2 if there are no other associated deficiencies and adrenal function is monitored.

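### Section 5.3 lets n. VII palsy treated with high-dose steroids restart at Grade 3, while Section 5.6 and the Section 6 neurologic table stop it

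*Combined protocol and SAP*

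**What the plan says.** Section 5.3 lists the criteria that end treatment, and Section 5.5 makes that list the basis for removal from study. One criterion concerns high-dose steroids: "Any toxicity requiring high dose corticosteroids except patients with grade 2 or 3 skin lesions, pruritis, thyroiditis, or n. VII palsy can be restarted". The restart is to follow a taper.

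Section 5.6 sets the conditions for resuming. It opens with a general limit: "Restarting applies only to Grade 2 events and some Grade 3 events (skin rash and thyroiditis"). For patients treated with corticosteroids it discontinues nivolumab at Grade 3 or above and repeats the same two exceptions: "Patients with Grade 3 thyroiditis and skin rash may continue therapy as for Grade 2 events". It does not name n. VII palsy.

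Section 6 has a separate table for neurologic events. Its Grade 3 row is off protocol therapy, with no exception. Its Grade 2 row first takes the patient off therapy if steroids are needed, then says that after resolution the patient may "resume at same dose level for peripheral isolated n. VII" palsy. The row does not say which of these two statements governs a Grade 2 palsy that needed steroids.

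Section 6 does refer back to the Section 5.3 exceptions, with "Off protocol therapy (exceptions noted in" Section 5.3), but only in the Grade 3 row for other immune-mediated events. The neurologic table has no such pointer.

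Section 13.1 makes the number of patients who stop for intolerable toxicity a primary tolerability measure. Section 13.3 uses the same event in the rule that stops enrollment.

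**The concern.** A site that works from Section 5.3 can restart nivolumab in a patient whose Grade 3 facial palsy needed high-dose steroids. A site that works from Section 5.6 or the neurologic table stops the drug for good. The first consequence is for the patient: whether someone is re-exposed after a severe neurologic immune event should not depend on which section was opened.

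The second is for the count. Under one reading the patient is a dose hold, and under the other a toxicity discontinuation. The Section 13.3 boundaries are 3 in the first 12 patients, 4 in the first 19, and 5 before the last patient is enrolled. One classification can therefore move the count onto a boundary.

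**Working it through.** **Text comparison, Grade 3 n. VII palsy after high-dose steroids**

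| Place | Outcome |
|---|---|
| 5.3, grade phrase read as covering the whole list | may restart (Grade 2 or 3) |
| 5.3, grade phrase read as covering skin lesions only | may restart, no grade limit stated |
| 5.6, general limit | not among the Grade 3 restarts |
| 5.6, steroid-treated patients | discontinue |
| 6, neurologic table, Grade 3 row | off protocol therapy |

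Both parsings of 5.3 include Grade 3. On the second, a Grade 2 limit has to be inferred from the other sections. The footnote to the neurologic table spares peripheral n. VII palsy from going off study, but its asterisk is attached to the Grade 1 and Grade 2 rows, not to Grade 3.

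**How often.** The adverse event list in Section 7.1 places facial nerve disorder, all grades, in the column for events under 3%. Expected number in 20 patients: below 20 × 0.03 = 0.6, before narrowing to Grade 3 on high-dose steroids. The documents do not give the Grade 3 share, so 10% and 50% are assumed.

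**Effect on the Section 13.3 rule.** Patients are taken in enrollment order with outcomes known at once. Enrollment stops at 3 or more through patient 12, at 4 or more for patients 13 to 19, and at 5 or more at patient 20. The probability is computed exactly by recursion on the running count. The background discontinuation probability is p = 0.10, the rate expected in Section 7.7.

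*Conditional on exactly one such patient*, with position averaged over 1 to 20, counted as a discontinuation with probability q, and the other 19 at p:

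| q | P(stop) |
|---|---|
| 0 (hold, never stopped later) | 13.7% |
| 0.25 (assumed later stop) | 18.3% |
| 0.50 (assumed later stop) | 23.0% |
| 1 (discontinuation) | 32.2% |

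The largest gap is 32.2 − 13.7 = 18.5 points. At other background rates, hold against discontinuation is 2.2% against 9.3% (p = 0.05), 33.6% against 56.8% (p = 0.15) and 55.3% against 75.9% (p = 0.20).

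*Weighted by occurrence.* If each patient has the disputed event with probability r, counting it as a discontinuation makes the per-patient probability p + (1 − p)r. The chance of at least one event in 20 is 1 − (1 − r)^20.

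| r | Source | p + (1 − p)r | P(at least one in 20) | P(stop) |
|---|---|---|---|---|
| 0 | all counted as holds | 0.1000 | 0 | 15.6% |
| 0.003 | 10% of 3% | 0.1027 | 5.8% | 16.6% |
| 0.015 | 50% of 3% | 0.1135 | 26.1% | 20.9% |

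The rise is 16.6 − 15.6 = 1.0 point or 20.9 − 15.6 = 5.3 points. The ceiling, with every facial nerve event Grade 3 on high-dose steroids (r = 0.03), is 26.6%, but nothing in the documents makes that plausible.

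**The case against.** The best defense is that Section 5.3 only removes one reason for stopping. Its wording is permissive, and it sends the reader to Section 6 and Appendix E for the specific rules. Section 6 in turn encourages use of its management tables and event-specific guidance. A site that follows those pointers reaches the Grade 3 neurologic row and stops the drug. Section 7.7 also requires sites to report Grade 3 and higher events to the coordinating center within 24 hours, so an unnoticed re-dose is unlikely. The neurologic flowchart in Appendix E is not visible in the text available here and may settle the matter.

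Much of this stands, and it is why the point is minor. It does not remove the conflict. Section 5.3 names the palsy as an event that can restart, no visible text says which section prevails, and the coordinating center needs one rule to apply.

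A reader might also infer a parallel conflict for Grade 2 colitis or pneumonitis treated with steroids. Section 5.6 says these events "should resolve to Grade 0 or baseline before retreatment", and the Grade 2 colitis row reads "Hold until Grade 0 or baseline. Consider steroid treatment > 7 days". The documents do not support that reading. For colitis, Section 6 states "Patients who require steroids should be taken off study treatment", and the Grade 2 pneumonitis row likewise removes patients who need steroids. The Section 5.6 sentence is a minimum condition for patients not already removed.

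**Conclusion.** The three places disagree about Grade 3 n. VII palsy after high-dose steroids, and they do so on either parsing of Section 5.3. Severity is minor. The reason to correct it is consistent patient safety, and consistent counting of toxicity discontinuations under Sections 13.1 and 13.3.

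The expected change in the chance of stopping enrollment is about 1 to 5 points. That assumes a 3% facial nerve event rate (the listed upper limit for all grades), Grade 3 shares of 10% to 50% that the documents do not supply, a 10% background rate, 20 patients and immediate outcomes.

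A reader might take the 13.7% against 32.2% contrast as the size of the problem. It is not: it presupposes that the rare event has occurred and that the held patient is never stopped for toxicity later. With an assumed 25% or 50% chance of a later stop, the gap falls from 18.5 to 13.8 or 9.2 points.

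**What to change.** 1. In Section 5.3, limit the n. VII palsy exception to Grade 2 isolated peripheral n. VII palsy. This matches Section 5.6 and the neurologic table, so Section 5.6 needs no change.
2. In the Grade 2 row of the neurologic table, state that the exception applies even when steroids were required. If that is not intended, delete n. VII palsy from the Section 5.3 exception instead.
3. Check both changes against the Appendix E neurologic flowchart.

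Do not add a general clause that Section 6 prevails over Section 5.6. Section 6 allows resumption after Grade 3 fever, renal toxicity and nausea or vomiting, which the general limit in Section 5.6 does not, so such a clause would loosen the restart rules.

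The cost is two wording changes, with no added procedures or patients. The downside is possibly one more permanent discontinuation, which would count toward the Section 13.3 boundary.

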#### 5.4 **Duration of Follow Up**

Patients will be followed for 1 year after removal from study or until death, whichever occurs first. Patients removed from study for unacceptable adverse event(s) will be followed until resolution or stabilization of the adverse event

